4.0 Study Design and Methodology

Design

This will be an open-label study. Patients will choose to participate in a Marijuana adjuvant treatment group, receiving marijuana in combination with standard opioid therapy.

The goal is to enroll at least 66 Hospice patients in the study.
Methodology

Patients will be notified of the study's existence through communication with the study's investigation team at time of admission. Patients will be screened for study eligibility—see section 6.0 for study eligibility factors—and if the patient is both eligible and interested in participating, the sub-investigator will discuss and review the informed consent form with the patient and obtain their signature; the patient will then have a consultation with a prescribing physician; and, if the physician has determined that medical marijuana is a viable option for that patient, registration with the Connecticut Medical Marijuana program will begin. For patients who have already been prescribed both marijuana and opioid medication upon admission to Hospice, signing the consent form will complete study enrollment.

Patients' initial opioid dose, dosing schedule and numeric pain score will be recorded. For the duration of the study (at least five days) changes in opioid doses and numeric pain scores will be tracked daily.

Marijuana will be administered to the patient via oral route three times daily for at least five days. Patients will receive CBD:THC product provided by NIDA.

On admission to the study, a modified Edmonton Symptom assessment scale to quantify baseline appetite, depression, nausea, vomiting, overall well-being, and anxiety.

Data Tracking: Primary objective tracking will include average numeric pain scores and number of opioid dosage increases and average daily opioid amount (mg equivalents of morphine).

Secondary objectives include Weight, Appetite, N/V, O2 Saturation, Self-reported data points from the modified Edmonton Assessment Scale.

Data Tracking Intervals: Primary objective tracking of pain will be daily every 4 hours (twice per shift). Secondary objective tracking as follows: Weight daily, Appetite every 8 hours (every shift), N/V, O2 saturation as reported by clinician documentation, Edmonton scale results three times weekly.

Analysis

Following the data collection phase, investigators will calculate average numeric pain scores, average number of increases in opioid dosage and average daily opioid amount (mg equivalents of morphine). Analysis will examine whether the addition of CBD/THC with opioid therapy had

a stabilizing effect or improvement in pain management (lower average numeric pain scores, few dosage increases, lower opioid doses and subsequently less opioid therapy needed)

Additionally calculations will include results of changes in weight, calculation of average changes in O2 saturation, and average changes in Edmonton-Scale scores for secondary data collection points.

Patient Selection to Ensure Validity

The study will enroll patients with a primary diagnosis (Table 1) of cancer and non-cancer with associated pain considered to have a terminal illness requiring end of life care, utilizing routine or as needed opioid therapy for pain.

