2.0 Background and Significance

The Connecticut Hospice, Inc., the first Hospice who served for four decades in the United States, recently received The Joint Commission 's first advanced palliative hospital certification without recommendations for improvement, embarks on a new study.

Hospice care (Johnson-Hurzeler 1998) involves managing symptoms and quality of life for patients whose life expectancy is less than six months. (Kruse 2013) A study involving 100 hospice inpatients revealed high incidence of many symptoms, including chronic pain (62% of patients), anorexia (58%), constipation (52%), nausea (37%), vomiting (24%), sleep issues (22%), and anxiety (19%). (Potter 2003) The majority of hospice patients are prescribed opioids for pain control. The typical process involves administering a certain dosage of opioids and, depending upon pain relief and side effects, the dosage (in mgs) may be adjusted accordingly in increments of 25%. Common side effects of opioid medications include constipation, nausea, sedation, respiratory depression, dependence, and death. (Bruehl 2014)

In studies to date, marijuana has shown promise as an adjunctive medication for patients who require opioids for pain management. (Karst 2009) An Australian study—POINT (Pain and Opioids in Treatment)—collected reports from 1,514 patients on the efficacy of marijuana in combination with opioids for management of pain from a diverse range of causes. (Degenhardt 2015) In general, patients reported that the combination of marijuana and opioids was more effective for pain relief than opioids alone. (Degenhardt 2015) Another study, which included 21 patients suffering from chronic pain, found increased efficacy in pain control with the addition of marijuana to opioid regimens; investigators concluded that addition of marijuana to opioid regimens may result in a lowered effective dose of opioids. (Abrams 2011) In the same study, investigators reasoned that marijuana facilitates the activities of opioids either by slowing opioid

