C
D

F
1.
2.

3.

4.

5.

6.

7.

8.

9.

10.

Initial Diagnosis: The first diagnosis of disease by a physician.

Recurrence: Subsequent diagnosis of same disease resulting from limited response to additional therapy expected and not durable.

Progression: Continuation of disease process.

Critical Clinical

Decision: Consensus decision made by physician, patient, and family that want to forego any continuing curative or rehabilitative treatment.

Footnotes

All patients participating in this study will be registered as medical marijuana patients in accordance with state law. This study will provide a basis for expanding the indications for which marijuana can legally be prescribed in the state of Connecticut, thereby benefiting additional patients.

The constituents of marijuana that have been most extensively studied for therapeutic purposes so far are A9-tetrahydrocannabinol (A9-THC) and cannabidiol (CBD). (Fine 2013) A9-THC acts primarily on Cannabinoid-1 receptors (CB1), which are most densely concentrated in central nervous tissue (brain and spinal tissue); CBD acts primarily on Cannabinoid-2 receptors (CB2), which exist mostly in peripheral tissues (all other tissues). (Fine 2013) Activation and inhibition of cannabinoid receptors affects pain perception, cognition and memory, locomotor activity, endocrine functions, temperature control and heart rate, nausea and vomiting, intraocular pressure, inflammation, and immune recognition and antitumor activity. (Fine 2013) Both CB-1 and CB-2 receptors are involved in regulating inflammatory pain. (Elikottil 2009) Relevantly for this study, A9-THC and CBD's actions upon cannabinoid receptors may reduce inflammation and pain. (Fine 2013) Furthermore, A9-THC has been shown to reduce nausea and vomiting. (Fine 2013) Whereas higher doses of A9-THC have been associated with adverse psychological effects—e.g. psychosis-like symptoms and motor and cognitive impairment—CBD seems to block, to a certain extent, those adverse psychological and cognitive effects of A9-THC. (Solowij 2014) Evidence of a physiological basis for the opposing effects of A9-THC and CBD emerged through an fMRI study in which researchers cross-referenced the behavioral effects of these substances with their respective fMRI images. (Bhattacharyya 2010)

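### Uncontrolled averages collected soon after hospice admission cannot separate a CBD/THC effect from changes over time in care, yet section 4.0 reads them as that effect

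*Combined protocol and SAP*

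**What the plan says.** **Recruitment and start (section 4.0, Methodology).** Patients hear of the study from the "investigation team at time of admission". Screening, consent and a physician consultation follow, and then, if the physician agrees, "registration with the Connecticut Medical Marijuana program will begin". No duration is given for any step and no day is set for the first capsule. There is a shorter route: "For patients who have already been prescribed both marijuana and opioid medication upon admission to Hospice, signing the consent form will complete study enrollment".

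**Design (section 4.0, Design).** "Patients will choose to participate in a Marijuana adjuvant treatment group, receiving marijuana in combination with standard opioid therapy". No other group is described. Baseline is a single initial record of opioid dose, schedule and pain score.

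**Opioids.** Section 5.0 accepts scheduled or as-needed opioid use and asks for no period of stable dosing. Section 2.0 describes usual practice: "depending upon pain relief and side effects, the dosage (in mgs) may be adjusted accordingly in increments of 25" per cent. Section 6.0 has a rule triggered by three scheduled opioid increases on the lower capsule regimen, so increases during capsule dosing are foreseen.

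**Analysis.** Sections 4.0 and 10.0 plan averages of pain score, number of opioid increases and daily morphine equivalents. Neither names a comparator, model, test or time adjustment. Section 4.0 nevertheless states: "Analysis will examine whether the addition of CBD/THC with opioid therapy had" a stabilising or improving effect on pain management.

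**The concern.** All three primary objectives in section 3.0 (pain scores, opioid increases, overall opioid use) can change with time in inpatient care. Opioid adjustment and other hospice care may lower pain soon after admission. Disease progression may raise pain or opioid need later. In a single group, either change is mixed with anything the capsule does.

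Two errors are possible. An inert capsule may appear to relieve pain because usual care relieved it. A useful capsule may appear to fail on opioid amount because need was rising anyway. A larger sample would not help, since this is bias and not imprecision. The stated goal in section 2.0 is to further substantiate marijuana's role in pain management, so the attribution matters.

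**Working it through.** **1. The plan's own figure.** The target of 66 (section 5.0) is the only design figure. The margin-of-error formula for a proportion, with 95% confidence, a 5% margin and a population of 700, gives n0 = 1.96² × 0.95 × 0.05 / 0.05² = 73.0, and n = 73.0 / (1 + 72.0/700) = 66.2. This matches only if the proportion is 0.95, which the plan does not state. The figure is not tied to pain or opioid change. It serves below only as n.

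**2. Timing.** Average stay is 12 days (section 5.0) and dosing lasts at least 5 days (section 4.0). For an average-stay patient, the first capsule comes at most 12 − 5 = 7 days after admission. A course at the early extreme covers about days 1–5; at the late extreme it covers about days 8–12, the end of the average stay. Section 5.0 treats that end as death, since it counts three days of life left after nine days.

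**3. Size of the possible error.** The documents give no SD and no expected change under usual care, so these are assumptions: SD of change 2, 2.5 or 3 points; fall from usual care d = 0.5 or 1 point; capsule effect zero; n = 66.

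SE = SD/√66. The chance that a before/after 95% CI lies wholly on the favourable side is Φ(d/SE − 1.96).

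| SD | SE | d = 0.5 | d = 1 |
|---|---|---|---|
| 2 | 0.246 | 53% | 98% |
| 2.5 | 0.308 | 37% | 90% |
| 3 | 0.369 | 27% | 77% |

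With d = 0 the figure is 2.5%.

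**4. Would a day-since-admission model solve it?** This was simulated with 66 patients, a wait of 1–4 days, five capsule days, patient SD 1.5, daily residual SD 1.2 with autocorrelation 0.4, and a 2-point early fall in pain. The model had patient and day effects plus a capsule indicator.

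- No drug effect: the before/after change averaged −0.79 to −1.19, depending on how days are indexed. The model gave about 0.
- Immediate constant effect of −1: the model gave about −1.
- Effect building linearly to −1 over five days, a mean of (0.2 + 0.4 + 0.6 + 0.8 + 1.0)/5 = 0.6 points of relief: the model gave about −0.03, favourable in roughly 2.5–5% of runs, much as for an inert capsule.
- Effect building to −1 over three days: the model gave about −0.3, favourable in about a quarter of runs.

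Every patient eventually receives the capsule, so no untreated patient anchors the later days, and the day terms absorb an effect that builds. The documents give no onset time, so the model cannot be relied on here.

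**The case against.** The study is labelled exploratory/pilot, and the plan specifies no before/after test or interval, so the percentages above describe an analysis it does not contain. Both points are correct. They lower the stakes and make the figures illustrative, but section 4.0 still attributes the averages to CBD/THC.

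Opioid dose is tracked daily and is itself a primary measure, so pain lowered by raising opioids would be partly visible. That stands as partial mitigation. But no joint or time-aligned analysis is planned, and pain falling on a flat opioid dose could still reflect titration before the first capsule or other inpatient care.

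A reader might infer that the capsule certainly starts while titration is taking effect. The documents do not say so: no start day is given, registration may delay it, and section 2.0 describes opioid adjustment in general, not the first inpatient days. Overlap with titration or late decline is a probable inference. It fits less well for patients already on marijuana at admission, who instead lack a pre-marijuana baseline.

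**Conclusion.** The concern holds as a limit on attribution. With one self-selected open-label group and averages only, the plan cannot separate a capsule effect from change over time in care. Under the stated assumptions, a 1-point fall from usual care would make an inert capsule look favourable in 77–98% of trials, and a 0.5-point fall in 27–53%. The size of any such fall is not in the documents.

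Three stronger readings are not supported:

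- That the bias has a known direction. Early relief and late decline can oppose each other, and pain and opioid use may be affected differently.
- That adjusting for day since admission would justify crediting CBD/THC. It can miss an effect that builds over days, and expectation in an open-label study starts with the first capsule and falls into the same coefficient.
- That the section 2.0 sentence, "This study will provide a basis for expanding the indications for which marijuana can legally be prescribed in the state of Connecticut", must go for this reason. It is background wording and does not follow from admission timing.

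**What to change.** 1. **Section 4.0, Methodology.** Record the date and time of admission and of the first capsule. Take charted pain scores and daily morphine equivalents from admission, not only from study entry.
2. **Section 10.0.** Report pain and morphine equivalents together, by day since admission and by day relative to the first capsule, with 95% CIs. Do this separately for patients with and without recent marijuana use.
3. **Section 4.0, Analysis.** Describe the averages as the course during treatment and do not attribute change to CBD/THC.
4. **Optional.** A model with patient, day since admission and capsule status may be added as an exploratory sensitivity analysis only. State its assumptions: an immediate constant effect, and a wait unrelated to the patient's course. State also that it can miss a gradual effect and cannot remove open-label expectation.

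The cost is a few extra chart fields and a weaker conclusion. No extra patients, visits or staff are needed.

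### The plan looks for lower pain and opioid use in one uncontrolled group but defines no comparator or baseline window; the only pre-treatment values it describes are one undated pain score and an initial opioid dose with schedule.

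*Combined protocol and SAP*

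**What the plan says.** Section 3.0 words the primary objectives as reductions: lower pain scores, fewer opioid dose increases, less opioid use overall. Section 4.0 describes an open-label study in which patients choose to join a single treatment group. No control group is described.

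Before treatment, Section 4.0 says that the patient's "initial opioid dose, dosing schedule and numeric pain score will be recorded". It does not tie this to admission, consent or first capsule. The modified Edmonton scale, by contrast, is explicitly taken on admission to the study.

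During treatment, Section 4.0 (Data Tracking Intervals) says "Primary objective tracking of pain will be daily every 4 hours (twice per shift". It also says that "changes in opioid doses and numeric pain scores will be tracked daily". Treatment length is given as follows: "Marijuana will be administered to the patient via oral route three times daily for at least five days".

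In the Analysis part of Section 4.0, the investigators will "calculate average numeric pain scores, average number of increases in opioid dosage and average daily opioid amount" and look for "lower average numeric pain scores, few dosage increases, lower opioid doses and subsequently less opioid therapy needed". Neither this text nor Section 10.0 gives a comparator, a change formula, a baseline window or a test for these outcomes.

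Four other statements bear on the point:
- Patients learn of the study at admission. After consent and a physician consultation, "registration with the Connecticut Medical Marijuana program will begin". Those already prescribed both marijuana and opioids complete enrolment by signing the consent form (Section 4.0).
- Opioid doses are typically adjusted in 25% steps (Section 2.0).
- Eligibility covers routine or as-needed opioid use and sets no minimum pain score (Section 5.0).
- The study is labelled exploratory/pilot (Section 1.0).

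**The concern.** With no control group, the pre-treatment value is the only internal reference against which a score or dose can be called lower. Here that reference is undefined, and the only candidate has three weaknesses:

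- **Precision.** One pain score on a fluctuating scale is a noisy anchor for a five-day average.
- **Timing.** Because the reading is undated, it could be taken close to admission, when pain may be at its worst and before ordinary opioid adjustment. Improvement that precedes the first capsule could then be counted as change on treatment.
- **Units.** An initial dose with a schedule and an average daily amount are the same quantity only if the schedule fixes how much is used in a day. For as-needed use it does not.

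At stake is whether the primary results can be read at all. A fall in pain could be noise, regression to the mean, opioid adjustment or drug effect. For as-needed users the change in opioid use cannot be computed like for like.

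**Working it through.** **The plan's own figures.** The plan gives no variance, effect size or precision for change in pain or opioid use, so there is nothing of that kind to reproduce. The target of 66 (Section 5.0) is used below only as n. How 66 was derived is a separate matter and does not affect this point.

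**Number of readings.** 24/4 = 6 pain scores per day, and 6 × 5 = 30 in the five-day minimum, against one initial score. For a patient followed only for the three-day minimum life expectancy in Section 7.0, it is 6 × 3 = 18. Opioid use is tracked daily, so there are about five values in five days, not 30.

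**Precision of mean change in pain.** Assumptions not in the documents: within-patient SD 2 points; 30 independent on-treatment readings; k independent baseline readings; no variation between patients in true change.

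SD of change = √(2²/k + 2²/30); 95% half-width = 1.96 × SD / √66.

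| k | SD of change | Half-width |
|---|---|---|
| 1 | √(4 + 0.133) = 2.033 | 0.49 |
| 2 | √(2 + 0.133) = 1.461 | 0.35 |
| 3 | √(1.333 + 0.133) = 1.211 | 0.29 |
| 6 | √(0.667 + 0.133) = 0.894 | 0.22 |

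Six readings in one day will be correlated. If they are worth only two or three independent ones, the relevant rows are k = 2 and k = 3.

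- *Same correlation on both sides.* If six readings count as two, 30 count as 10. The half-widths are then 1.96 × √(4 + 0.4)/√66 = 0.51 with one baseline reading and 1.96 × √(2 + 0.4)/√66 = 0.37 with the averaged one.
- *True change varies between patients.* With an assumed SD of 1.5, add 2.25 to the variance. One reading gives 1.96 × √6.383/√66 = 0.61; six independent readings give 1.96 × √3.05/√66 = 0.42.
- *Fewer on-treatment readings.* With 18 instead of 30, the k = 1 value is 1.96 × √(4 + 0.222)/√66 = 0.50. The single baseline reading dominates.

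**Bias in mean change in pain.** This was simulated with no drug effect and no opioid adjustment (400,000 draws per setting). Assumed: mean score 5, SD 2.5, correlation between two readings in the same patient 0.4, 0.6 or 0.8.

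- *No selection on the initial score:* mean change 0.00, whether 1 or 30 later readings are averaged. The imbalance in counts does not cause bias.
- *Initial score effectively 5 or more at entry:* mean change −1.2, −0.8 and −0.4 for the three correlations. This agrees with (1 − correlation) × mean excess over the population mean: the excess is 2.5 × √(2/π) = 1.99, giving 1.20, 0.80 and 0.40. A nominal two-sided 5% test with 66 patients would reject in about 100%, 99.6% and 86% of trials.
- *Effective cut-offs of 4 to 6:* −0.3 to −1.6.
- *Baseline as the mean of six readings taken after the selecting one:* mean change 0.00 in every setting.

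**Direction of opioid adjustment.** Raising the opioid dose between the initial reading and the first capsule tends to lower later pain scores. The same step raises later daily amounts relative to the initial dose. Continued increases on treatment raise both the amount and the count of increases. The distortion favours benefit for pain and works against it for the two opioid outcomes.

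**Units for opioid use.** For scheduled opioids, dose × doses per day gives a daily amount, so a comparison is possible. For as-needed use, dose and schedule do not determine milligrams per day, so there is no matching baseline. The count of dose increases has no pre-treatment counterpart for anyone.

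**The case against.** Several stronger readings are tempting, and the documents do not support them.

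- *That the plan judges change against a single reading.* It names no comparator. The documented gap is an undefined comparator; the initial reading is merely the only pre-treatment value described.
- *That setting one reading against about 30 biases the result towards improvement.* It does not. Bias needs entry at high pain. Section 5.0 sets no score threshold, so such selection is implicit at most: admission with pain that requires opioids.
- *That the initial reading certainly precedes the registration step and pre-dose adjustment.* The reading is undated, and its sentence follows the registration text. Patients already prescribed marijuana have no registration wait.
- *That an ordered dose is set against milligrams actually taken.* The plan says average daily amount without saying ordered or taken. For scheduled opioids the recorded schedule largely closes the gap.
- *That all three primary outcomes are flattered.* Upward titration works against the two opioid outcomes.

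It is also fair to say that every magnitude here rests on assumed variances, that the gain in precision shrinks once patients differ in true change, and that an exploratory pilot need not meet a confirmatory standard. All of that stands. It limits the size and certainty of the point but does not supply the missing comparator or a usable opioid baseline for as-needed users.

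**Conclusion.** The point holds, at the level of something that should be changed. Resting only on the text: no comparator or baseline window is defined for the primary outcomes, the only pre-treatment values described are undated and taken once, and there is no like-for-like opioid baseline for as-needed users.

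Resting on assumptions: using the single pain score as baseline gives a half-width of about 0.49 points, against 0.22 to 0.35 for an averaged baseline (within-patient SD 2, n = 66), or 0.61 against 0.42 if true change varies between patients with SD 1.5. A spurious fall in pain of roughly 0.3 to 1.6 points is possible, but only if entry in effect selects high scores. Without that selection, regression to the mean contributes nothing. Whatever the baseline, a change in this single self-selected group cannot be attributed to the drug.

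**What to change.** In Sections 4.0 and 10.0:

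1. Start the 4-hourly pain charting at consent.
2. Define baseline pain as the mean of all 4-hourly scores in the 24 hours before the first study capsule, excluding the admission score, which is kept for description.
3. Define baseline opioid use as total morphine equivalents taken in the same 24 hours, and state that the on-treatment daily amount is also the amount taken.
4. Report within-patient change from these baselines with a 95% CI. Report the number of dose increases as an on-treatment count, since it has no baseline counterpart.
5. Report patients already using marijuana separately, because their baseline is not marijuana-free.
6. State that, without a control group, changes are descriptive and not attributable to the drug.

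The cost is a few lines of text and up to a day of earlier charting in patients who are already inpatients. Patients dosed soon after consent will have fewer than six baseline readings, so the number available should be reported. The window moves the reference point past any adjustment made before it, but it does not remove later time trends or continuing opioid titration. Some regression to the mean may also remain if the baseline readings are correlated with the score at entry.

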3.0 Objectives

Primary

1. Improve pain management as identified by decreased overall numeric pain scores
2. Reduce opioid dosage increases
3. Reduce overall opioid utilization

Secondary

Evaluate changes in patient weight, appetite, nausea and vomiting, O2 saturation, feelings of well-being, anxiety, and depression.

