5.0 Study Population

Adult (≥18 years of age), non-pregnant, alert and oriented hospice inpatients. Subjects must take opioids for pain management either routinely scheduled or on an as needed basis to qualify.

Inclusion / Exclusion Criteria

Included: alert adults (age 18+) requiring opioids for pain management (routine or as needed) with a cancer diagnosis or non-cancer diagnosis as their terminal illness as defined in Table 1 .

Excluded: pregnant women, children (patients < 18 years of age), minimally or unresponsive patients unable to take oral medications, and agitated combative patients.

Sample Size

66 patients is the target.

The average length of stay at The Connecticut Hospice, Inc. is twelve days. At the end of each nine day cycle (i.e. the time by which the average patient has three days to live), we can expect roughly thirty-five out of thirty-nine inpatients to take opioid medication(s) to manage pain.

Since the study will happen over about 180 days, this means the population size for the length of the study should be about 700 patients.

Therefore, assuming a 95% confidence interval, a 5% error margin, and a statistical significance level of .05, we have calculated a target sample size of 66 patients.

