10.0 Statistical Analysis Plan

The calculation of the average daily numeric pain scores, the average number of opioid dosage increases, and average daily opioid amounts (mg of morphine equivalents) will be evaluated. In addition, the secondary measures of, oxygen saturation, heart rate and body weight, findings from the Edmonton numeric assessment scale: nausea/vomiting, appetite, depression, anxiety and overall well-being will be examined.

There will be a database for tracking all primary and secondary data.

Sample size determination

See sample-size calculation and justification under "Study Population" (section 6.0).

Missing, unused, and spurious data

Missing, unused, and spurious data will be documented ongoing and noted in the final study results.

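### The three primary outcomes are read as bare averages, with no interval, no any-or-all rule, and an undefined stabilizing effect counted as favourable, so unchanged pain under an inert drug could be reported as benefit.

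*Combined protocol and SAP*

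**What the plan says.** Section 3.0 lists three primary objectives: "Improve pain management as identified by decreased overall numeric pain scores", "Reduce opioid dosage increases" and "Reduce overall opioid utilization". They are numbered, with pain first, but nothing says that the numbering is a hierarchy. The data-tracking text in section 4.0 carries all three side by side: "Primary objective tracking will include average numeric pain scores and number of opioid dosage increases and average daily opioid amount".

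The analysis is described in two places. In section 4.0, "investigators will calculate average numeric pain scores, average number of increases in opioid dosage and average daily opioid amount", and the question asked of these averages is whether there was "a stabilizing effect or improvement in pain management (lower average numeric pain scores, few dosage increases, lower opioid doses". Section 10.0, the statistical analysis plan, begins "The calculation of the average daily numeric pain scores", adds the other two averages, and says that they will be evaluated. Neither place gives a test, interval, contrast with baseline, averaging window, success threshold, or rule for combining the three outcomes. Stabilization and few increases are not defined.

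Inferential terms appear only in the sample-size paragraph of section 5.0, "assuming a 95% confidence interval, a 5% error margin, and a statistical significance level of .05", where they are tied to no outcome.

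Four other parts of the protocol bear on the point:

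- Section 2.0 says that opioid doses are usually adjusted in steps of 25% according to pain relief and side effects.
- Section 4.0 describes one open-label group that patients choose to join. It records the starting opioid dose, schedule and pain score, and follows patients for at least five days.
- Section 1.0 labels the study exploratory or pilot.
- Section 2.0 says that the study should further substantiate a role in pain management and serve as a basis for widening the legal indications.

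**The concern.** A reading rule has to be able to come out unfavourable. Here that is doubtful for each outcome.

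- **Pain score.** If opioids are adjusted until pain is controlled, a steady pain score is what usual care aims for, whatever the study drug does. Counting stability as favourable credits the drug with that result.
- **Dose increases.** No count from before treatment and no control rate exist, so no number of increases can be shown to be few or many.
- **Daily opioid amount.** A baseline exists, but with no interval any fall in the average, however small, can be called lower.

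The any-or-all rule and the meaning of stable are both left open, so they could be settled after the data are seen. What is at stake is whether the final report can separate a real change from noise or from routine titration. The stated wish to support wider legal indications makes that matter more than the pilot label suggests.

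**Working it through.** **The plan's own figures.** The plan gives no error rate or precision for any primary outcome, so there is none to reproduce on this point. Its only inferential figure is the target of 66. The usual survey formula is n0 = z²p(1−p)/e², corrected for a population of 700 by n = n0/(1 + (n0−1)/700). With z = 1.96 and e = 0.05:

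- p = 0.5 gives n0 = 384.2 and n = 248.3, that is 249.
- p = 35/39 gives n0 = 141.4 and n = 117.8, that is 118.
- p = 0.95 gives n0 = 73.0 and n = 66.2. The documents never state this proportion.

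On any of these inputs the formula gives precision for one proportion, and none of the three primary outcomes is a proportion. The .05 and 95% in section 5.0 therefore govern nothing in the analysis. Below, n = 66 is taken as stated.

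**Which outcomes can move favourably.** Pain score and opioid amount have a recorded baseline (section 4.0). The increase count starts from zero and has no reference value. The illustration therefore uses two outcomes.

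**Illustration with zero mean change.** Each average has a 0.5 chance of falling. Suppose that one favourable direction is enough.

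- Independent outcomes: 1 − 0.5² = 0.75.
- Assumed correlation ρ = 0.5: P(both rise) = 1/4 + arcsin(0.5)/(2π) = 1/4 + 1/12 = 1/3, so 1 − 1/3 = 0.667.

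Suppose that stable also counts, taken as a worsening of no more than 0.10 SD (an assumed band). With √66 = 8.124, each outcome passes with probability Φ(0.10 × 8.124) = Φ(0.812) = 0.792. At least one of two independent outcomes passes with probability 1 − 0.208² = 0.957.

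**Same condition, stricter reading.** If all three must improve, treating the increase count as though it had a reference value, the probability is 0.5³ = 0.125 for independent outcomes. Over assumed correlations from −0.3 to 0.8 it runs from 5% to 35%.

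**Drift unrelated to the drug.** Take an assumed drift of 0.25 SD, two independent outcomes, one favourable direction sufficient, and no credit for stability. Φ(0.25 × 8.124) = Φ(2.031) = 0.979.

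| Assumed drift | Chance of a favourable reading |
|---|---|
| Pain falls, opioid amount rises | 1 − 0.021 × 0.979 = 0.979 |
| Pain flat, opioid amount rises | 1 − 0.5 × 0.979 = 0.511 |
| Both worsen | 1 − 0.979² = 0.042 |

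**What an interval would give.** The half-width of a 95% interval for a mean change at n = 66 is t(0.975, 65)/√66 = 1.997/8.124 = 0.246 SD, about ±0.25 SD before losses.

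**What an interval would not give.** If pain falls by 0.25 SD from usual care alone, a two-sided 95% interval lies wholly on the favourable side with probability of about Φ(2.031 − 1.96) = 0.53.

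**The case against.** The strongest reply is that the protocol never says that any one outcome is enough. The bracketed list in section 4.0 goes on, joined by a conjunction, to less opioid therapy being needed, and it can be read as one joint pattern. That stands. The text sets no rule in either direction, so an any-one rule cannot be put forward as the plan's rule.

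A reader might go further and infer that a favourable conclusion is likely under an inert drug, at 87.5% (1 − 0.5³). The documents do not support this. The figure needs the any-one reading, exactly zero drift, and a baseline for the increase count, which is not recorded. In dying patients whose opioids are being adjusted, no drug effect is not the same as no mean change, and the drift table shows how far the chance can move.

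A reader might also cite a 14.3% familywise error (1 − 0.95³), or 7.3% in the favourable direction (1 − 0.975³). These describe three .05 tests that nobody plans, in a study labelled exploratory, where formal familywise control is often not required.

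The exploratory label does not answer the rest. Estimates still need intervals, and a favourable reading still needs a definition, particularly given the uses set out in section 2.0.

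Making the opioid claim wait for a pain result would be a debatable choice. Two of the three objectives concern opioids, and titration can hold pain flat while opioid need changes. The fix therefore does not require that gate.

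**Conclusion.** The concern holds in a limited form. Three primary outcomes are evaluated as averages with no interval and no any-or-all rule, and an undefined stabilizing effect counts as favourable. With opioids adjusted to pain relief, no comparator, and no earlier count of increases, following the plan as written could report unchanged pain or few increases as benefit when the drug does nothing. This is more than missing detail, because the favourable reading includes the result that usual care is meant to produce.

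No single probability measures the problem. The 75% and 66.7% rest on zero mean change, an any-one reading and the two outcomes with a baseline. The 12.5% rests on an all-three reading with independent outcomes. The correlations, the stability band and the drifts are assumptions, since the documents give none. The width of the range shows that the conclusion depends on a rule the plan does not state. It does not establish that a false favourable conclusion is likely.

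**What to change.** Amend the Analysis part of section 4.0 and section 10.0 as follows.

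1. Report the patient-level change from baseline in mean pain score and in daily morphine equivalents, over a fixed window such as the first five days, each with a two-sided 95% interval. Call a change an improvement only if its interval excludes zero in the favourable direction.
2. Name pain as the single primary outcome, which agrees with the primary goal in section 2.0. Otherwise keep both outcomes and adjust for two. For example, 97.5% intervals at n = 66 have a half-width of about 0.28 SD (2.295/8.124).
3. Report the rate of dose increases descriptively, with an interval.
4. Delete the stabilizing effect as a favourable reading. Otherwise allow it only if the upper 95% limit for the pain change lies below a worsening margin fixed before data review.
5. Word all conclusions as change over time, not as drug effect. The intervals guard against chance, not against drift or titration, and do not cure the missing control.

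The cost is wording only, since the data are already to be collected. The downside is small: fewer outcomes can be reported as favourable. Adjusting for two outcomes also widens the intervals slightly.
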